3.0 Inclusion/Exclusion Criteria

We will recruit a total of 225 patient-caregiver dyads, randomizing 112 dyads each to the intervention and control (usual care) arms.

Eligibility criteria for patients include:

- age 65 or older
- community-dwelling in the Indianapolis metropolitan area (assisted living facility acceptable; long stay NH residents excluded);
- have an established diagnosis of dementia of any etiology as determined by memory care practice and confirmed by research team review of medical record;

- dementia in the moderate (FAST stage 5) to severe stage (FAST 6-7); and
- have a primary caregiver available and willing to serve as both an informant on the patient's status and as a subject him or herself.

Exclusion criteria for patients include:

- resident living in a nursing facility, Skilled Nursing Facility, Long Term Acute Care (LTC), Personal Care Home
- patient expressing dissent
- being diagnosed with a serious mental illness such as bipolar or schizophrenia
- Hospice enrollment (Addition IRB Approved: 5/13/2019)

Eligibility criteria for caregivers include:

- reside locally;
- English-speaking;
- live with patient or have at least 2 contacts per week on average with the patient (1 face-to-face);
- designation as the patient's primary caregiver; and
- has not been diagnosed with a serious mental illness such as bipolar or schizophrenia.

Recruitment

Dyads will be recruited from Indiana Discovery Network for Dementia (http://indydiscoverynetwork.org/) memory care practices in the Indianapolis area. Utilizing established memory care practices allows us to rely on their diagnostic assessment (confirmed by record review by research team) and to efficiently recruit eligible subjects. Our customary and successful recruitment methods utilize the Indiana Network for Patient Care (INPC) and the Indiana Health Information Exchange (IHIE) to identify potentially eligible patients with dementia based on ICD-9 and ICD-10 diagnostic codes and prescriptions for anti-dementia drugs in medical records. Memory care providers then help narrow the list of potential dyads to be approached and allow access to clinic schedules. Research assistants then arrange to meet dyads at a clinic appointment or offer a home visit to discuss the study.

Research staff will ask caregivers a series of questions to assess the patient's cognitive and functional status. This information will be used to determine the severity of the patient's dementia using the FAST. Only patients meeting criteria for FAST stage 5 (moderately severe) or stage 6-7 (severe) will continue in the enrollment process.

An IN-PEACE research assistant, with approval from the practitioner, will obtain informed consent of the patient's legally authorized representative (LAR) for study participation. (The LAR and caregiver will be two individuals in a few cases. For example, one adult child may hold power of attorney for the patient and another adult child may be the primary caregiver. In those cases, the LAR gives proxy consent for the patient and the caregiver gives informed consent for their own participation.) Because the severity of the patient's dementia is advanced, while decision making capacity of the patient will be assessed using the teach-back method, we expect most patients will lack decisions making capacity to provide informed consent If the patient expresses meaningful dissent, patient will not be enrolled, even if the LAR is willing to consent.

Potential subjects can self-refer for this study. Approved study brochures will be distributed at community events, such as conferences, meetings, or other contacts with the public. Interested subjects will be asked to provide their name, email address, telephone number and mailing address. A Research Assistant will contact potential subjects with the contact information provided to screen for inclusion/ exclusion criteria to determine eligibility. We may email/ direct mail consent statement to interested participants, upon request. The mail/email template will include the scripted language previously approved with the screening/ enrollment script, and approved IN-PEACE brochure. An Email/Direct mail template has been approved by the IRB.

4.0 Enrollment/Randomization

After enrollment and baseline assessments are completed, subjects will be classified according to disease severity (moderately severe (FAST = 5) or severe (FAST = 6-7).

Stratified randomization based upon dementia severity will be used to assign patient-caregiver dyads to either the intervention or usual care arm.

5.0 Study Procedures

Timeline

The study will take place over five years with a six month start-up time period. It will take 24 months to accrue the target sample size utilizing a rolling enrollment and intervention delivery process. Subjects receive the intervention for 24 months and the last outcome assessment is also at 24 months. In the final year of the study, in addition to completing analyses and preparation of manuscripts, we would plan a competitive renewal proposal to continue following the subjects in order to address aims relating to care in the last days/weeks of life, hospice referral, and resource utilization.

	YEAR 01		YEAR 02	YE	AR 03	YEAR 04		YEAR 05	
Start-up activities									
Subject accrual		rolling en							
		months	Intris						
Intervention		each dyad receives 24 months of the intervention							
Delivery									
Outcome		each dyad assessed at baseline, 3, 6, 9,12, 15, 18, 21,							
assessments		and 24 months							
Analysis;									
manuscripts									

Assessments: Measures and Schedule of Administration

Domain	Measure	Items	Schedule (months)									
Domain	IVICASUI C		0	3	6	9	12	15	18	21	24	EOL
Patient (PT) measu	res											
Patient related mea	sures assessed directly by research	assista	nt									
Cognition	MOQA	30	Х				Х				Х	
Patient related mea	sures obtained via caregiver (CG) in	terview	(proxy	y repo	ort)							
Neuropsychiatric Symptoms	Neuropsychiatric Inventory Questionnaire (NPI-Q) ⁹¹	12	Х	Х	Х	Х	Х	Х	Х	Х	Х	
Symptom Management	Symptom Management at the End of Life in Dementia (SM-EOLD) ⁹²	9	Х	Х	Х	Х	Х	Х	Х	Х	Х	Х
Comfort Assessment	Comfort Assessment in Dying with Dementia (CAD-EOLD) ⁹²	15										Х
Activities of Daily Living	Physical Self-Maintenance Scale ¹⁰⁶	13	Х	Х	X	Х	Х	X	X	X	Х	
Functional status	FAST staging ⁸⁰ (caregiver report, ADLs)		Х									
Medical comorbidity	Checklist of conditions ¹¹	10	Χ									
Caregiver measures												 
CG Distress from Neuropsychiatric Symptoms	Neuropsychiatric Inventory Questionnaire (NPI-Q) ⁹¹ (CG reaction portion of instrument)	12	Х	х	х	Х	Х	×	х	Х	х	
Depression (CG)	Patient Health Questionnaire (PHQ-8) ⁶⁵	9	Х	Х	Х	Х	Х	Х	Х	Х	Х	Х
Caregiver Strain	Caregiver Strain Index ¹⁰⁷	13	Х				Х				X	
Satisfaction with Care	Satisfaction with Care at the End of Life in Dementia (SWC-EOLD) ⁹²	10	Х	Х	Х	Х	Х	Х	Х	Х	Х	Х

Respondent Burden	Benefit and Burden Scale ¹⁰⁸	4		Χ	Х	Χ	Х	Х	Х	Х	Х	Х
Other data from CG	interview											
Advance Care Planning (ACP)	Questions on specific directives	10	Х	Х	Х	Х	Х	Х	Х	Х	Х	
Hospice	Hospice utilization	4										Х
Socio-demographics (PT/CG)	age, race, sex, education, marital, job status, income	10	Х									
Medical Record Rev	riew and INPC/IHIE Data Stream											
Etiology of Dementia	Chart review	n/a	X									
ER/Hospitalizations	Health information exchange data	n/a					Х				Х	Х

Intervention

Intervention arm. Multi-disciplinary clinical team meetings with PI, co-investigators (MA, KK, SH, AMT), and care coordinators will be held weekly throughout the study. During these meetings, the team will review data from the baseline assessments to

- identify triggers for interventions,
- make protocol and other treatment recommendations, and
- communicate these to the care coordinator for dyads randomized to the intervention arm.

Caregivers will be contacted by the care coordinator within one week following the clinical team meeting or within ten days of the baseline assessment.

Care coordinators will initiate caregiver protocols to address unmet needs and individualized areas of focused care, overcoming barriers to provision of excellent palliative care. The assigned care coordinator will be the primary contact and will follow the dyad throughout the study with backup support and cross-coverage (i.e. social worker may call in RN for help with nursing issues and vice versa).

The coordinator will direct the caregiver to the INPEACE manual (provided at enrollment that contains PREVENT materials relating basic dementia care needs, caring for the caregiver, management of neuropsychiatric symptoms, and the IN-PEACE materials on goal setting and advance care planning, pain evaluation and management, navigating the hospital, feeding difficulties, and hospice transitions, including appropriate industry materials). Specific tools to aid in the evaluation and management of pain include a list of nonverbal indicators of pain⁷⁷ and a card with the lowa Pain Thermometer⁷⁸ on one side and Faces Pain Scale⁸¹ on the other. These will aid in rating pain and in communicating about it with the care coordinators and physicians. Caregivers will be instructed that they can refer to the management techniques in the manual on their own and should have it available when speaking with the care coordinator on the phone. Caregivers will be asked to contact the IN-PEACE care coordinators throughout the study at times of acute events or symptom changes, hospitalization, or with questions, concerns, and referral/resource requests.

Care coordinators will record information on all contacts and interventions in templated notes in the web-based tracking system, both to provide information for follow up, as well as to provide descriptive information on numbers and types of contacts, protocols triggered, and interventions carried out.

Care coordinators will initiate contact with caregivers at 1, 2, and 4 weeks after enrollment and then monthly thereafter. At each contact, the DCC will use, open-ended questions about the patient's most bothersome symptoms, and the caregiver's assessment of the patient's level of pain. Responses indicating symptoms that are frequent or causing distress in the patient or caregiver trigger the appropriate protocols for managing those symptoms. Non-pharmacological and behavioral strategies have an early and important role in the protocols. Several of the protocols have the equivalent of laboratory "panic values," findings that would trigger a more intensive response from the care coordinator. For example, new onset pain that is severe would result in a call to the patient's primary care physician and discussion about whether the patient should be seen in the office or even the emergency room. Some of the protocols may trigger follow up sooner than the next scheduled Revision Date: 4/10/2020

monthly contact. Using pain as the example again, the care coordinator will contact the caregiver within 72 hours and continue to intervene if there has not been at least a 50% reduction in the rating of pain.

Some protocols, such as feeding/weight loss and planning for hospice, may be triggered either by a decline in functional status or a hospital admission, rather than a symptom. Goal setting and advance care planning will be addressed repeatedly, first at enrollment and then as major changes in clinical status occur. The clinical team will meet weekly with the care coordinators to discuss scheduled contact reports, caregiver initiated contacts and questions, and review and revise plans of care. Recommendations of the clinical team will be tracked in the care coordinator's contact database with follow up appointments set. For more urgent medical issues, care coordinators can contact the clinical team representative between meetings for advice or recommendations to the caregiver to seek care from the primary care provider or emergency room.

Table 2 outlines barriers to palliative care in dementia, possible solutions, and the aligned protocols developed for IN-PEACE to address the barriers.

Table 2: Palliative Care in Dementia: Barriers and Solutions

Barrier to excellent palliative care in dementia ⁸²	Potential Solution(s)	IN-PEACE Protocols/Interventions				
"Dementia not a terminal illness"	Reframing advanced stages as terminal	Prognostic Information				
Lack of advance care planning	Ongoing care planning with caregivers	Goals of Care / Advance Care Planning				
Poor symptom management	Proactive assessment and attentive management	Proactive Assessment (behaviors/psychological; pain; other symptoms; caregiver mood/distress) Symptom Protocols Caregiver Support Protocols				
Difficult decisions: antibiotics and tube feeding	Information about benefits & burdens; context of goals of care, alternatives	Goals of care / Advance Care Planning Feeding / Weight Loss Navigating Hospital				
Avoidable hospital use Burdensome treatments/transitions Underutilization of hospice	Support care at home Increase discussion of benefits of palliative care and hospice options	Symptom Protocols Goals of Care / Advance Care Planning Transition to Hospice				

The information collected by the care coordinators via telephone that are either scheduled or initiated by caregiver concerns at any time will be reviewed at weekly interdisciplinary team meetings. This information will consist primarily of reports of behavioral problems, pain and other bothersome symptoms, and caregiver well-being. This "clinical data" is used solely to help manage care of the patient and caregiver and are not part of the separately scheduled research outcome assessments. The team also will review any interventions carried out or ordered by the care coordinator, additional services recommended, and assess initial responses to these actions, if already available. The team may further modify the care plan.

The two Research Assistants will be blinded to the randomization assignment and will not be involved in any meetings or discussions about intervention subjects. The research manager (LH) will review outcomes measures and if there are any values that exceed pre-specified levels, she will bring those to the attention of the PI. These are similar in nature to "urgent" or "panic" values in laboratory blood test reports or X-ray reports requiring attention of a clinician and represent a safety feature for all dyads, control and intervention, and not a part of the IN-PEACE intervention. For example, any severe pain or pain associated with a fall or other trauma will result in a call to a physician and either scheduling of an appointment or instructions to go to the emergency room.

The revised plans of care generated by the care coordinators and the supportive care clinical team are intended to affect the study outcomes and should be thought of as integral components of the

intervention. Tailoring protocolized treatment actions to the particular patient's needs is the standard for multi-component trials of collaborative care interventions.

The care coordinators will send periodic updates, in the mode and frequency as requested, to the patient's primary care provider. Most participating providers in the Indianapolis area will be familiar with electing secure email, fax, phone, or text pager for their preferred modes of communication because of the INPC, IHIE, and other ongoing, innovative efforts, such as those sending pending lab results from hospital and emergency room visits to physicians' offices. The team will communicate with the primary care provider to request referrals to other specialists and when initiating protocols such as pain and hospice conversations.

Additionally, up to 25 caregivers, randomized to the intervention arm, will be asked to participate in a one-time qualitative interview aimed to explore the attitudes toward and experience with decisions to deprescribe medications of caregivers for community dwelling patients with moderate-severe AD with a focus on learning from the caregivers the ethical considerations that they take into account. The study will employ semi-structured interviews (in-person or by telephone) and qualitative methods for analyzing transcriptions of the recorded interviews.

Usual care arm.

Dyads randomized to "usual care," will be receiving care that is likely of a higher quality than the typical patient with dementia in the community setting given the involvement of IDND memory care practitioners. However, control dyads will not have access to the dementia care coordinator proactively making contact, assessing needs, and implementing IN-PEACE management protocols as the intervention subjects will have. Caregivers in the usual care group will have access to educational and informational materials from the local chapter of the Alzheimer's Association and other community resources and will be reminded of their availability. Protocols will be in place for appropriate referral when research assistants' assessments elicit information about severe symptoms or distress.

Data Collection

Baseline and final outcome assessments will be done in person at the subjects' home or the memory care practice site. Other outcome assessments will be done by phone or in the home, based on caregiver preference. The outcome measures for both intervention and usual care groups will be collected at baseline and months 3, 6, 9, 12, 15, 18, 21, and 24 post-enrollment. Caregivers also will be interviewed 6 to 8 weeks after the patient's death if that occurs during the course of the study. Data will be collected by research assistants who have not been involved in the ongoing management of the patients and are blinded to dyad assignment to intervention or usual care arm.

Data obtained from the one-time qualitative interview will be audio-record and transcriptions will be used for data analysis using grounded theory.

6.0 Reporting of Adverse Events or Unanticipated Problems involving Risk to Participants or Others

The safety monitoring for this study will be the responsibility of the Principal Investigator ([name]), study biostatistician ([name]), and Safety Officer, who is external to Indiana University, and who are knowledgeable about dementia and older adults. Specifically, the Safety Officer will be selected based on the knowledge and experience in dementia, caregiving, palliative care, and clinical research studies. The Safety Officer, PI, Program Officer, and study biostatistician will meet by phone semi-

annually during active recruitment, data collection and analysis. Topics the group will review include: inclusion/exclusion criteria; participant accrual; and adherence and modifications to research protocols and procedures. Preliminary data trends on the primary and secondary outcomes will be discussed. In addition, the group will review procedures for protection of human subjects, including study withdrawals and adverse events reports and devise stopping rules, as applicable, based on potential harms and adverse events.

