2.0 Rationale and Specific Aims

Aim 1: To test the effect of the IN-PEACE intervention on patients' neuropsychiatric symptoms (e.g., agitation/aggression, anxiety, repetitive behaviors). Mixed effects models will be used to compare repeated NPI-Q scores obtained at 3, 6, 9, 12, 15, 18, 21, and 24 months. Repeatedly measured NPI-Q scores will be the dependent variable in the model.

Aim 2: To test the effect of the IN-PEACE intervention on patients' overall symptom outcomes. Analyses in this aim will use repeatedly measured SM-EOLD scores over 24 months of follow-up as the dependent variable in the mixed effects model, similarly to the approach described for Aim 1.

Aim 3: To test the effect of the IN-PEACE intervention on caregivers' distress and mood. Aim 3 analyses will use repeatedly measured caregiver NPI-Q distress scores and caregiver PHQ-9 over 24 months of follow-up as the dependent variables in separate mixed effects models, similar to the approach for Aim 1.

Aim 4: Evaluate the effect of the IN-PEACE intervention on ER/hospital use. ER/hospitalization events will be obtained from accessing electronic medical records maintained by the Indiana Health Information Exchange (IHIE) and the Indiana Network for Patient Care (INPC). Poisson regression models will be used to compare rates of any ER/hospitalization event between the two groups while adjusting for dementia severity and significant baseline variables that differ between the two groups.

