8.0 Statistical Considerations

The proposed study is a RCT comparing the multi-component, supportive care intervention (IN-PEACE) to usual care. Primary and secondary outcomes will be collected at baseline, 3, 6, 9, 12, 15, 18, 21, and 24 months. A patient reaches study endpoint by either completing 24 months of follow-up or other conditions described in Subject tracking. We will compare baseline characteristics between the intervention group and the control group using two sample *t*-tests for continuous normally distributed variables, Wilcoxon test for continuous non-normal variables, or chi-square tests for categorical variables. Variables found to be significantly different at the α =0.05 level will be adjusted in the comparisons of all outcome variables.

Table 4: Power estimates for significant interactions between group and time in the mixed effect

models with 85 patients per group.

Outcome Measures	. Ou	d Change in tcome th interval)	Power			
	Intervention	Intervention Usual Care				
Aim 1: NPI-Q Severity	-0.45	0.2	80%			
Aim 2: SM-EOLD	1.31	0*	85%			
Aim 3a: Caregiver NPI-Q distress	-0.39	0.08	80%			
Aim 3b: Caregiver PHQ-9	-0.22	0.16	81%			

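### Is the Aim 3b caregiver depression outcome left undefined because the schedule says PHQ-8 while Aim 3 and Table 4 say PHQ-9?

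*Combined protocol and SAP*

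**What the plan says.** The combined protocol and SAP names the caregiver depression instrument in three places.

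- Section 2.0, Aim 3, makes it one of two modelled outcomes: "caregiver NPI-Q distress scores and caregiver PHQ-9 over 24 months of follow-up as the dependent variables in separate mixed effects models".
- Section 8.0, Table 4, gives it a power row, "Aim 3b: Caregiver PHQ-9". The expected change per 3-month interval is -0.22 under the intervention and 0.16 under usual care, and power is 81% with 85 per group.
- Section 5.0, in the schedule of measures, has a single caregiver depression row. Its label is "Patient Health Questionnaire (PHQ-8", its Items cell is 9, and it is marked at baseline, every three months to month 24, and in the EOL column.

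No section gives the item content, scoring or score range, or says that one form replaces the other.

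**The concern.** Caregiver depression is one of four outcomes with a power figure, and the schedule is the only place that ties a depression form to visits. If the suffix is taken as the number of items, a literal reading of the label has staff collect eight items while the analysis models a nine-item score, which could not then be computed. The other three Table 4 outcomes (NPI-Q severity, SM-EOLD and caregiver NPI-Q distress) match the schedule by name; only Aim 3b does not. At stake would be the definition of the Aim 3b score and whether the expected changes and the 81% in Table 4 refer to the score actually collected.

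**Working it through.** **1. Which form do the entries support?** Taking the suffix as the item count:

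| Entry | Where | Points to |
|---|---|---|
| Outcome name in Aim 3 | Section 2.0 | nine items |
| Outcome name in Table 4 | Section 8.0 | nine items |
| Items cell of the depression row | Section 5.0 schedule | nine items |
| Label of the same row | Section 5.0 schedule | eight items |

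The nine-item reading requires one wrong character. The eight-item reading requires three wrong entries, one of them in the same row as the label. That is not proof, but it ranks the explanations. It also weakens the literal-reading worry: the row as printed lists nine items, so the modelled score becomes impossible to compute only if the Items cell is wrong as well.

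**2. Can the 81% be reproduced?** No. The documents give no standard deviation, within-person correlation or slope variance, and state no alpha for the outcome tests. One can only solve backwards. Assume a two-sided alpha of 0.05 and a simple comparison of mean per-interval change between two groups of 85:

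- difference = 0.16 - (-0.22) = 0.38
- implied SD = 0.38 / [(1.960 + 0.878) × √(2/85)] = 0.38 / (2.838 × 0.1534) ≈ 0.87

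This SD is an output of the stated power, not a check on it. Under the same set-up, an SD of 0.8 would give 87% and an SD of 1.0 would give 70%.

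**3. Would an eight-item form change the power?** It depends on how the difference and the SD move together, which the documents do not say. Two illustrations, each assuming equal item contributions:

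- Both scale by 8/9: the ratio of difference to SD is unchanged, and power stays at 81%.
- Only the difference scales by 8/9 (0.38 × 8/9 = 0.338) and the SD stays at 0.87: power is about 71%.

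The second case removes an item's share of the effect but none of its variability, so it is a pessimistic illustration and not an expected consequence.

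**4. Does the study size rest on this row?** Table 4 uses 85 per group throughout, with power of 80% (Aim 1), 85% (Aim 2), 80% (Aim 3a) and 81% (Aim 3b). If the target was 80% (an assumption, since none is stated), Aims 1 and 3a are the binding rows. Removing the Aim 3b row would not reduce the 85.

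**5. Does the form affect the validity of the comparison?** Section 5.0, Data Collection, has outcome measures collected in both arms at the same months by research assistants blinded to assignment. An eight-item or nine-item total, collected alike in both arms, can be fitted with the same model and gives a fair comparison of randomised groups. The form affects the name and scale of the outcome, not bias or type I error.

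**The case for a change.** The best counter-argument is that leaning towards nine items is not the same as settling it. The document has been revised over time: Section 3.0 carries "Hospice enrollment (Addition IRB Approved: 5/13/2019" and Section 5.0 carries "Revision Date: 4/10/2020". A half-completed switch from one form to the other is therefore conceivable. The rest of the depression row reads cleanly although other parts of the table are damaged, so a misread digit cannot simply be presumed. A reader of the Aim 3b result should also know which score it refers to.

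Part of this stands. The documents do not establish which form was administered, and the sponsor could confirm it in a moment. But the dated revisions say nothing about this measure: the first concerns an exclusion criterion, and the second breaks into the middle of a sentence and looks like a page footer. Nor does any text suggest that the form changed during follow-up or differed between arms, which is what it would take to disturb the analysis. The point about reporting is fair, but it is met by naming the collected form in the report.

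**Conclusion.** The inconsistency is real but clerical. Most likely one character in one schedule label is wrong, or was misread from the PDF; three other entries agree on nine items. No effect on the 81% power or on the Aim 3b inference is shown.

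No change to the plan follows, because the gap closes itself when the data arrive: the dataset will hold either eight or nine item responses per visit, and the analyst will total them, fit the planned model and report the score under its proper name. If the eight-item form turned out to be the one used, the outcome name and item count would need tidying and the Aim 3b row of Table 4 would be a planning figure for a closely related score. The test and the randomised comparison would stand.

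This rests on two assumptions: that the suffix denotes the item count, and that a single form was used in both arms throughout. Nothing in the documents contradicts the second; on the first, the only mismatch is the disputed label itself.

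### Does handing out the IN-PEACE manual at enrolment, before randomisation, put intervention material into the usual-care arm?

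*Combined protocol and SAP*

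**What the plan says.** Section 4.0 (Enrollment/Randomization) sets the order of events: "After enrollment and baseline assessments are completed, subjects will be classified according to disease severity", and then "Stratified randomization based upon dementia severity will be used to assign patient-caregiver dyads to either the intervention or usual care arm". Allocation therefore follows both enrolment and baseline.

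Section 5.0 (Study Procedures, Intervention) describes the manual: "The coordinator will direct the caregiver to the INPEACE manual (provided at enrollment that contains PREVENT materials". Its contents include basic dementia care, caregiver self-care, neuropsychiatric symptoms, pain, advance care planning, feeding, hospital stays and hospice. It can be used without the coordinator: "Caregivers will be instructed that they can refer to the management techniques in the manual on their own".

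This description is part of a block that opens "Intervention arm. Multi-disciplinary clinical team meetings with PI". In that block, the clinical team's recommendations go to the coordinator; staff are to "communicate these to the care coordinator for dyads randomized to the intervention arm".

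The usual-care paragraph of Section 5.0 says that "control dyads will not have access to the dementia care coordinator proactively making contact", or assessing needs and applying the IN-PEACE protocols. It then names what controls can use instead: materials from the local Alzheimer's Association chapter and other community resources. It does not mention the manual.

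On blinding, Section 5.0 states: "The two Research Assistants will be blinded to the randomization assignment".

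**The concern.** Set side by side, Sections 4.0 and 5.0 look inconsistent. If enrolment is a step completed before randomisation, a manual supplied at enrolment reaches every dyad. It is not a trivial leaflet: its topics match most of the IN-PEACE protocols in Table 2 and bear on the outcomes of Aims 1 to 3, and caregivers may use it alone. Controls who held it would receive part of the intervention, which would pull the estimated effects towards no difference.

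The alternative reading seems to carry a risk of its own. If the manual is for the intervention arm only, someone must hand it over once the arm is known. Research assistants obtain consent (Section 3.0, Recruitment) and collect the study data, with baseline done in person (Section 5.0, Data Collection). If they delivered the manual, they would learn the allocation. That would matter because the patient symptom measures are caregiver reports taken at interview.

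At stake would be the separation of the arms or the blinding of the assessors.

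**Working it through.** **Step 1. Which arm does the manual sentence describe?** It falls in the block labelled for the intervention arm, before the separate usual-care paragraph. Its subject is the coordinator, and caregivers are to have the manual at hand when they speak with the coordinator by phone. Control dyads have no coordinator contacting them. The caregiver in that sentence is therefore an intervention caregiver.

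**Step 2. What does enrolment mean in Section 5.0?**

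| Where | What is timed from enrolment | Consequence if enrolment strictly precedes randomisation |
|---|---|---|
| Intervention arm | Coordinator contacts at 1, 2 and 4 weeks | Clock starts before anyone has a coordinator |
| Intervention arm | Goal setting and advance care planning first addressed | An IN-PEACE protocol (Table 2) starts before allocation, so controls get it too, against the usual-care paragraph |
| Data Collection | Outcome visits at months 3 to 24, both arms | No conflict; the word marks the start of follow-up |
| Intervention arm | Manual supplied | Controls get it too |

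The strict meaning breaks the goal-setting row in the same way as the manual row. The meaning that fits all four rows is the start of participation. For intervention-arm items, this means once the dyad is in that arm.

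**Step 3. Is there an unavoidable choice between contamination and unblinding?** The two harms need different readings. Contamination needs the manual to go to everyone before allocation, and a handout of that kind reveals no arm. Unblinding needs a research assistant to hand it out after allocation, and no sentence says so. The sentence does not name who supplies the manual. A third arrangement fits all the text: intervention dyads receive it after allocation from someone other than a research assistant.

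**Step 4. Can the loss be sized?** Table 4 gives 80% power for Aim 1 with 85 patients per group and changes per 3-month interval of −0.45 and 0.2, a difference of 0.65. It gives no SD, within-patient correlation, alpha or sidedness, so the 80% cannot be reproduced. Assuming a two-sided alpha of 0.05 and a two-sample comparison of change per interval, the SD implied by the stated power is

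SD = 0.65 / [(1.96 + 0.84) × √(2/85)] = 0.65 / (2.80 × 0.1534) = 1.51.

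Putting this SD back returns 80% by construction, so it is no independent check. If a fraction f of the effect also reached controls,

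power = Φ(2.80 × (1 − f) − 1.96), and n per arm for 80% power = 85 / (1 − f)².

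| Assumed f | Power at 85 per group | Analysed n per arm for 80% |
|---|---|---|
| 10% | 71% | 105 |
| 20% | 61% | 133 |
| 30% | 50% | 174 |
| 50% | 29% | 340 |

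The difference of 0.65 and the SD cancel out of the power formula. The power column depends only on the starting 80%, the assumed alpha and f, so it would be the same for any trial with 80% power. It says nothing about whether this manual reaches controls or how much it would do there.

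**The case for a change.** The best case for a change is that arm separation and assessor blinding are central to this trial, and that the wording is imprecise on both. The block heading makes intervention-only provision the likely intent, but it does not settle when the manual is handed over or by whom. The coordinator's contacts are described as telephone contacts, whereas the consent and baseline steps involve research assistants. Using one word for a step before randomisation in Section 4.0 and for the start of the intervention in Section 5.0 invites misreading. The usual-care paragraph never expressly withholds the manual. A clarification would take two sentences.

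Much of this stands as description. The literal timing is inconsistent with Section 4.0, the hand-over is not described, and no sentence excludes the manual from usual care in so many words.

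The step from there to a flaw does not stand. Not naming the person who hands over the manual does not assign the task to a blinded assistant, and the blinding rule for research assistants already argues against it. Naming different materials for controls, and denying them the coordinator who applies the IN-PEACE protocols, is good evidence that the manual is not part of usual care. The power figures cannot tip the balance because the fractions behind them are assumed.

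**Conclusion.** No change is needed. This is a gap in wording that trial staff can fill sensibly: the arm-specific text shows that the manual belongs to the intervention arm, and the blinding rule shows who should not be handing it out after allocation. No stated rule or figure has been shown to give a wrong result, and nothing in Table 4 or the planned models depends on when the manual changes hands.

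The size of any dilution cannot be established from the documents. The fall from 80% to between 71% and 50% holds only if controls actually received the manual, if it alone delivered 10% to 30% of the effect, and if the test is two-sided at 0.05. None of these is stated. The conclusion rests on reading enrolment in Section 5.0 as the start of participation, which fits the timing of coordinator contacts, goal setting and outcome visits. It would change only with evidence that control dyads were given the manual or that research assistants delivered it after allocation. The documents contain no such evidence.
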